5.2 Withdrawal of subjects from study

Subjects **must be withdrawn from the trial** (treatment and procedures) for the following reasons:

- Subject withdraws consent from study treatment and study procedures. A subject must be removed from the trial at his/her own request or at the request of his/her legally acceptable representative. At any time during the trial and without giving reasons, a subject may decline to participate further. The subject will not suffer any disadvantage as a result.
- Subject is lost to follow-up.
- Death.

Subjects **may be** withdrawn from the study for the following reasons:

- The subject is non-compliant with study drug, trial procedures, or both; including the use of anti-cancer therapy not prescribed by the study protocol.
- Pregnancy. Pregnancy will be reported as an SAE. (Note: subjects who have been withdrawn from treatment with study drug because of pregnancy should not undergo CT scans [with contrast]/MRI or bone scans while pregnant.)
- If, in the investigator's opinion, continuation of the trial would be harmful to the subject's well-being.
- Severe allergic reaction to sorafenib (such as exfoliative erythroderma or Grade 3 or 4 hypersensitivity reaction).
- The development of a second cancer.
- Development of an intercurrent illness or situation which would, in the judgment of the investigator, significantly affect assessments of clinical status and trial endpoints.
- Deterioration of ECOG performance status to 4.
- Use of illicit drugs or other substances that may, in the opinion of the investigator, have a reasonable chance of contributing to toxicity or otherwise skewing trial result.

Any subject removed from the trial will remain under medical supervision until discharge or transfer is medically acceptable.

In all cases, the reason for withdrawal must be recorded in the CRF and in the subject's medical records.

Details for the premature termination of the study as a whole (or components thereof [e.g. centers, treatment arms, dose steps]) are provided in Section 10 (Premature termination of the study).Screen Failures/Dropouts

A subject who discontinues study participation prematurely for any reason is defined as a “dropout” if the subject has already assigned to treatment/run-in/wash-out; administered at least one dose of study drug.

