A subject who discontinues study participation for reasons other than toxicity after receiving sorafenib but not the Y-90 procedure is inevaluable and will be replaced. Subjects who are discontinued from the study early due to toxicities will be counted in the toxicity assessment.

A subject who, for any reason (e.g. failure to satisfy the selection criteria), terminates the study before the time point used for the definition of “dropout” (see above) is regarded a “screening failure”. Replacement

No withdrawn subjects will be replaced.

6. Treatment[s]

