8.1 Statistical and analytical plans

Statistical consideration for 2012-0870: study of sorafenib plus theraspheres for extrahepatic hepatocellular carcinoma (redesign, 20 patients have enrolled in study 2012-0870)

This is a phase II study of sorafenib plus theraspheres for extrahepatic hepatocellular carcinoma (EHC). The primary objective is to evaluate the progression-free survival (PFS), where the progression-free survival will be measured from the start of therapy until failure to disease progression or death.

Historical data showed that the median PFS was 4.1 months for EHC patients treated with sorafenib alone. We expect that the combination treatment would improve the PFS. A maximum of 40 will be recruited for the study at a rate of 1-2 patients per month. The study will monitor toxicity and futility.

Futility monitoring

The primary endpoint PFS will be monitored using the method of Thall et al. (2005), and we will stop enrolling patients to the study if, based on the available data, we have little reason to believe that the median PFS of the combination therapy (m_E) is more than that of sorafenib alone (m_S) in the historical data, which was 4.1 months. Formally, we'll stop the study early if

$$\text{Prob}(m_E > m_S | \text{data}) < 0.15$$

That is, if there is less than 15% chance the median PFS of the combination therapy is more than that of sorafenib, the trial will be stopped. Where m_S represents the median PFS for sorafenib alone in the historical data with an inverse gamma distribution $IG(11, 41)$, which corresponds to a mean of 4.1 months and a variance of 1.87. m_E represents the median PFS for the study combination therapy, assuming the prior for m_E is $IG(2.17, 4.8)$, which has the same mean as m_S but with a much larger variance (i.e. 99) to reflect much greater uncertainty about the median PFS of the combination therapy of sorafenib and theraspheres.

Futility monitoring will start once 20 patients have been enrolled. Assuming an accrual rate of 1.5 per month and an additional follow-up of 12 months, the operating characteristics for the futility stopping rule under various true states are summarized in the following table 8, with results based on 5000 simulations.

Table 8. Operating characteristics for the time-to-progression monitoring

True Median Time to progression	Pr(stop early)	Average Number of Patients Treated (25th, 75th percentiles)
2	0.993	21 (20, 20)
3	0.529	31.4 (20, 40)
4	0.100	38.3 (40, 40)

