5	0.017	39.7 (40, 40)

If the trial continues to maximum accrual of 40 patients and maintains sufficient follow-up to observe 25 events (PD/death) with a median PFS of 4.1 months, then a 95% credible interval for median PFS would extend from 2.76 to 6.08 months.

Toxicity Monitoring

In addition, toxicity will be monitored closely in all patients using the method of Thall et al (1995). The interim monitoring will be first conducted after the first 20 patients have been evaluated and then be repeated after each cohort of 5 patients. Denote the probability of toxicity by θ_E , where toxicity is defined as any non-hematological Grade 3 or greater complications attributable to the treatment. We assume $\theta_E \sim \text{beta}(0.6, 1.4)$. We will stop the

trial if at any point $\Pr(\theta_E > 0.30 \mid \text{data}) > 0.85$. That is, we will stop the trial if, at any time during the study, we determine that there is more than 85% chance that the toxicity rate is more than 30%. Stopping boundaries corresponding to this stopping rule are listed in table 9.

Table 9: Stopping boundaries for toxicity monitoring

Among These Number of Patients	Recommend Stopping if Toxicity Observed in n or more patients
20	9
25	11
30	12
35	14

Table 10: The operating characteristics for toxicity monitoring are summarized in the following table

True toxicity probability	Probability of early stop	Sample size percentiles (10, 25, 50, 75, 90)
0.1	0.0001	40 40 40 40 40
0.2	0.017	40 40 40 40 40
0.3	0.211	25 40 40 40 40
0.4	0.651	20 20 25 40 40
0.5	0.938	20 20 20 20 30

Multc Lean V2.1 and OneArmTTE Version 4.1.1 were used for the trial design.

Futility monitoring in CTC website

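### Section 5.2 both replaces and does not replace patients who leave before Y-90 for non-toxicity reasons, and does not say for which endpoint they are inevaluable; Section 8.1 names no PFS analysis set

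*Combined protocol and SAP*

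**What the plan says.** Section 5.2 carries two statements a few lines apart. Under Screen Failures/Dropouts, a subject who discontinues "for reasons other than toxicity after receiving sorafenib but not the Y-90 procedure is inevaluable and will be replaced". Under Replacement: "No withdrawn subjects will be replaced". Between them stands one sentence that names an endpoint: "Subjects who are discontinued from the study early due to toxicities will be counted in the toxicity assessment". The same section lists death, loss to follow-up and consent withdrawal ("Subject withdraws consent from study treatment and study procedures") as reasons for mandatory withdrawal.

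Section 7.4 makes everyone with at least one dose of study treatment valid for safety, and the synopsis analysis plan likewise includes all treated patients in the toxicity analysis.

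In Section 8.1 PFS is the primary objective, and "the progression-free survival will be measured from the start of therapy until failure to disease progression or death". Sections 3 and 4 put Y-90 3 to 5 weeks after sorafenib begins. On numbers, "A maximum of 40 will be recruited for the study". On timing, "Futility monitoring will start once 20 patients have been enrolled", whereas the toxicity looks begin "after the first 20 patients have been evaluated". Neither the futility rule nor the primary analysis paragraph says which patients are in the PFS analysis, or how patients who never receive Y-90 are handled.

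**The concern.** The replacement sentence may be meant as an exception to the general one, but the text does not say so. Separating discontinued from withdrawn subjects does not rescue it: a patient who dies, withdraws consent or is lost before Y-90, for a reason other than toxicity, meets both descriptions.

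The larger issue is what the inevaluable label does. Applied to safety, it removes patients whom Section 7.4 includes. Applied to PFS, it conditions on reaching Y-90, which happens after the clock has started. Excluding patients who died or progressed in that window raises the estimated median. Excluding patients who left event-free lowers it, because only those who had survived the window progression-free are removed. Section 6.3 gives a concrete route to the second case: a patient on sorafenib whose lung shunting or gastrointestinal flow cannot be corrected does not receive Y-90, and the label would apply if that patient then left the study.

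PFS drives both the futility rule and the comparison with the historical 4.1 months. With no named set, the same data could support different medians and different stopping decisions, and the choice could be made after the data are seen.

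**Working it through.** **Step 1: reproduce Table 8 with every enrolled patient counted.** Inputs from Section 8.1: prior IG(2.17, 4.8) for the combination median, IG(11, 41) for the historical median, stop if the posterior probability is below 0.15, looks from 20 patients, maximum 40, accrual 1.5 per month, 12 months of further follow-up. Assumed: exponential PFS, evenly spaced entry, a look just before each new entry and one at the end. With d events and total follow-up T, the posterior is IG(a, b), a = 2.17 + d, b = 4.8 + ln2 × T, and Prob(m_E > m_S) is the Beta(a, 11) distribution function at b/(b + 41).

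| True median | Table 8 | Reproduced |
|---|---|---|
| 2 | 0.993 | 0.994 |
| 3 | 0.529 | 0.533 |
| 4 | 0.100 | 0.101 |
| 5 | 0.017 | 0.017 |

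The published figures therefore fit an analysis of all enrolled patients from the start of therapy, with no exclusions modelled (20,000 runs, simulation standard error about 0.004).

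**Step 2: hypothetical effect on the median.** Let q be the share of pre-Y-90 events dropped, and c the share of patients event-free at the Y-90 date who leave and are dropped. The documents fix neither; both are assumptions. With a 4-week gap (0.92 months) and true median 4.1:

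- Early events: E = 1 − 2^(−0.92/4.1) = 0.144.
- Retained share: S = E(1 − q) + (1 − E)(1 − c).
- Weight of patients past the gap: wL = (1 − E)(1 − c)/S.
- Retained median: 0.92 + (4.1/ln2) × ln(2wL).

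Example, q = 50%, c = 0: S = 0.072 + 0.856 = 0.928; wL = 0.922; median = 0.92 + 5.915 × ln(1.845) = 4.54. At q = 100%, wL = 1 and the median is 4.1 + 0.92 = 5.02.

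**Step 3: hypothetical effect on futility stopping at true median 3.** Same simulation, with dropped patients replaced without delay.

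| q | Median, c = 0 | Median, c = 10% | Pr(stop), c = 0 | Pr(stop), c = 10% |
|---|---|---|---|---|
| 0 | 4.10 | 4.01 | 0.533 | 0.584 |
| 10% | 4.19 | 4.10 | 0.488 | 0.535 |
| 50% | 4.54 | 4.49 | 0.291 | 0.318 |
| 100% | 5.02 | 5.02 | about 0.08 | about 0.08 |

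(The median columns use true median 4.1, the stopping columns true median 3.) The two effects on the median cancel when q = c. The exponential-model estimate, which is closer to the Bayesian analysis, moves less: 4.16, 4.39 and 4.74 at q = 10%, 50% and 100% with c = 0. At c = 0, as q goes from 10% to 50%, Pr(stop) runs from 0.50 to 0.34 with a 3-week gap and from 0.48 to 0.25 with a 5-week gap.

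**Step 4: test the remedy.** Keep everyone who starts sorafenib and censor event-free leavers at 4 weeks. If leaving is unrelated to prognosis, Pr(stop) at true median 3 is 0.533, 0.535 and 0.526 with 5%, 10% and 20% leaving, against 0.533 with no leavers. If 20% leave and have twice the hazard of the others, it is 0.35, against 0.48 with full follow-up. If they have half the hazard, it is 0.71 against 0.48.

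**The case against.** The strongest reply is that PFS is probably not affected at all. Futility looks count enrolled patients, PFS starts with therapy, Table 8 reproduces with everyone counted, and the only endpoint named beside the label is toxicity. This stands as the likelier reading. A reader might go further and infer that the primary median will be inflated, or the futility rule weakened. The documents do not support that: no text applies the label to PFS, no leaver counts are given, and nothing suggests that any of the 20 patients already enrolled was excluded.

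Two other inferences should be resisted. One is that replacement must break the ceiling of 40. Section 8.1 says 40 recruited, so replacements can be found within that number. The other is that no scan precedes Y-90, so almost no early progression could be seen. Section 6.3 lists liver CT or MRI in the pre-TheraSphere evaluation. The baseline scan might serve, but the timing is not stated. Progression is also not a listed withdrawal reason in Section 5.2, so a low q is plausible without being established.

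The reply does not remove the core. Confining the label to toxicity avoids the PFS problem only by creating a conflict with Section 7.4, and the two replacement sentences still oppose each other.

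**Conclusion.** Section 5.2 contains a plain contradiction on replacement and an evaluability label with no endpoint, and Section 8.1 leaves the PFS set unnamed. That much rests on the text alone and should be fixed. Any effect on PFS is conditional on the label being applied there and on assumed shares of leavers, so the figures show what is at stake and do not forecast it. Under exponential PFS and a 4-week gap the upper case, every pre-Y-90 event dropped, is a median of 5.02 instead of 4.1 months and a stopping probability of about 0.08 instead of 0.53 at a true median of 3. At q = 10% the change is 0.09 months and about 0.04 in stopping probability. The direction depends on who leaves.

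**What to change.** In Section 5.2, reconcile the two replacement sentences, consistently with the maximum of 40 recruited, and state that the inevaluable label removes nobody from the PFS analysis or from the Section 7.4 safety set.

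In Section 8.1, define the PFS set, for futility looks and the final analysis alike, as all patients with at least one sorafenib dose, timed from first dose. Count progression or death before Y-90 as an event. Keep patients who leave event-free and censor them at their last progression-free assessment.

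The cost is a few sentences. A few patients without Y-90 will enter the primary analysis, and the reported median may be slightly lower. Censoring leavers is unbiased only if leaving is unrelated to prognosis, as Step 4 shows, so they should be followed for PFS and survival where consent allows. If any of the first 20 patients was set aside, follow-up would have to be retrieved and may not be recoverable after consent withdrawal.

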6.1 Treatments to be administered

6.2 Sorafenib Dosage and administration

Include the following regarding sorafenib therapy:

Subjects will be instructed on the proper administration of sorafenib. Sorafenib tablets should be taken 12 hours apart, at approximately the same time each morning and evening.

Sorafenib tablets should be taken without food, at least 1 hour before or at least 2 hours after a meal, and with up to 240 mL (approximately 1 cup or 8 oz) of water. Consumption of grapefruit and grapefruit juice should be avoided while receiving study drug.

Sorafenib tablets are manufactured by Bayer HealthCare. The 200-mg tablet formulation contains sorafenib tosylate and the excipients croscarmellose sodium, microcrystalline cellulose, hypromellose, sodium lauryl sulfate, and magnesium stearate. The tablets have a film coating comprised of hypromellose, polyethylene glycol, titanium dioxide, and red ferric oxide, which has no effect on the release rate of the active ingredient, sorafenib tosylate. The tablets are un-debossed, salmon colored, weigh approximately 350 mg each, and are 10 mm (millimeter) round in shape.

The chemical name for sorafenib tosylate is 4-{4-[3-(4-Chloro-3-trifluoromethyl-phenyl)-ureido]-phenoxy}-pyridine-2-carboxylic acid methylamide-4-methylbenzene-sulfonate, and its molecular weight is 637 daltons. The structure of sorafenib is depicted in [Figure 6-1](#).

[figure not shown]

Figure 6-1: Structure of Sorafenib (BAY 43-9006)

Sorafenib tablets do not need to be protected from light. They are sufficiently stable with regard to light, oxidation, thermal stress, and hydrolytic degradation. The formulation is presented as an immediate release (IR) dosage form, i.e., the active ingredient is completely dissolved under in vitro test conditions within a short period of time. Dose Modification for management of adverse events

6.2.1.1 Dose Reduction Levels

The starting dose of sorafenib is 400 mg twice a day. Study medication will be administered daily on a continuous basis.

Doses will be delayed or reduced for clinically significant hematologic and non-hematologic toxicities that are related to protocol therapy according to the guidelines shown in the Dose Delays/Dose Modifications table that follows. Dose modifications will follow predefined dose levels: Dose adjustments for hematologic toxicity are based on the blood counts obtained in preparation for the day of treatment.

Table 1: Dose modification levels for sorafenib

Dose	Sorafenib
Starting Dose	400 mg twice daily
-1	400 mg once daily
-2	400 mg every other day

6.2.1.2 Dose modification for hematologic toxicities

Recommended Dose Modification for Hematologic Toxicities [Table 2]

Toxicity	ANC/AGC (x 10 ⁹ /L)	Hemoglobin (g/dL)	Platelets (x 10 ⁹ /L)	Sorafenib
Grade 1	≥ 1.5	< LLN – 10.0	≥75	Treat on time

				No change
Grade 2	≥ 1.0 to < 1.5	$< 10.0 - 8.0$	≥ 50 to < 75	Treat on time No change
Grade 3	≥ 0.5 to < 1.0	$< 8.0 - 6.5$	≥ 25 to < 50	Treat on time Reduce by one dose level
Grade 4	< 0.5	Life-threatening consequence; urgent intervention indicated	< 25	Delay sorafenib until toxicity resolves to Grade 2 or less then Reduce by two dose levels
Febrile Neutropenia				Sorafenib held until toxicity has resolved to Grade 2 or less; when sorafenib is restarted, reduce by one dose level

ANC - absolute neutrophil count ; AGC - absolute granulocyte count

- If no recovery after 30 day* delay, treatment should be permanently discontinued unless treating physician determines subject is deriving clinical benefit.
* Modify according to study specific cycle length.

6.2.1.3 Dose modification for non-hematologic toxicities

Table 3: Recommended dose modification for non-hematologic toxicity (excluding hypertension and hand foot skin reaction, diarrhea and fatigue).		
Grade	Dose Interruption	Dose Modification
Grade 0-2	Treat on time	No Change
Grade 3	Interrupt until \leq Grade 2	DECREASE one dose level
Grade 4	OFF protocol therapy	OFF protocol therapy

 • If no recovery after 30 day* delay, treatment will be discontinued unless subject is deriving clinical benefit * Modify according to study specific cycle length. 		

6.2.1.3.1 Prevention/management strategies for diarrhea and fatigue

Diarrhea and fatigue are common side effects of sorafenib. The same dose-modification algorithm used for skin toxicities can be used to address these toxicities. However, the

preventive/management strategies for diarrhea and fatigue should be consistent with local standards (e.g., anti-diarrheals and optimized hydration status for diarrhea).

6.2.1.4 Hand-foot-skin reaction

Table 4: Recommended dose modification for hand foot skin reaction		
Toxicity Grade		Suggested dose modification
Grade 1	Any occurrence	Maintain dose level and consider topical therapy for symptomatic relief
Grade 2	1 st occurrence	Maintain dose level and consider topical therapy for symptomatic relief If no improvement within 7 days, see below
	No improvement within 7 days or 2 nd occurrence	Interrupt until resolved to Grade 0-1 When resuming treatment, decrease dose by one dose level
	3 rd occurrence	Interrupt until resolved to Grade 0-1 When resuming treatment, decrease dose by two dose levels
	4 th occurrence	Discontinue treatment permanently
Grade 3	1 st occurrence	Interrupt until resolved to Grade 0-1 When resuming treatment, decrease dose by one dose level
	2 nd occurrence	Interrupt until resolved to Grade 0-1 When resuming treatment, decrease dose by two dose levels
	3 rd occurrence	Discontinue treatment permanently

At first occurrence of HFSR, independent of grade, prompt institution of supportive measures such as topical emollients, low potency steroids, or urea-containing creams should be administered.

Recommended prevention/management strategies for skin toxicities consistent with HFSR are summarized below.

Table 5: Recommended Prevention/Management Strategies for Skin Toxicities Consistent with Hand-Foot-Skin-Reaction	
Toxicity Grade	Practical Prevention / Management Strategies for HFSR
Grade 0 (Preventive strategies)	
 • Maintain frequent contact with trial physician to ensure early diagnosis of HFSR. • Practical prevention strategies 
 ○ Pedicure^a for subjects with pre-existing hyperkeratosis. ○ Subjects should avoid hot water, and clothing or activities that can cause friction on the skin. ○ Moisturizing cream should be applied sparingly. • Padded gloves and open shoes with padded soles should be worn to relieve pressure points.
Grade 1 Any occurrence	
 • Continue preventive strategies and in addition: 
 ○ Soak hands in cool water. ○ Apply petroleum jelly to moist skin. • In the case of hyperkeratotic lesions, exfoliate the hands or feet and apply moisturizing cream immediately afterwards.
Grade 2 Any occurrence or Grade 3 Any occurrence	
 • Continue supportive/management measures and add analgesic(s) for pain.
a: Pedicure should be done by a podiatrist.	

6.2.1.5 Treatment-emergent hypertension

Hypertension is a known and potentially serious AE associated with sorafenib treatment. Subjects will check blood pressure at home, on a weekly basis through the first 4 weeks of therapy. Thereafter, blood pressure will be monitored on Day 1 of each cycle. Subjects with pre-existing hypertension will monitor blood pressure at home daily basis.

Blood pressure measurements that are out of the normal range must be reported by the treating physician.. Blood pressure measurements considered out of the normal range are diastolic pressure > 90 mm Hg and/or systolic pressure > 140 mm Hg, or a 20 mm Hg increase in diastolic pressure if the previous measurement was within normal limits.

The dose-modification schedule to be followed in the event of treatment-emergent hypertension is outlined below. The choice of anti-hypertensive medication to be used in cases of treatment-emergent hypertension will be at the investigator's discretion and based on site-specific treatment guidelines as applicable. All anti-hypertensive medications used for

the management of treatment-emergent hypertension should be recorded in the subject's records.

Once a dose-reduction modification has been made for treatment-emergent hypertension, NO dose re-escalation will be allowed.

Table 6: Management of Treatment-Emergent Hypertension	
Grade of Event (NCI-CTCAE v4.0)	Management/ Next Dose
Grade 1	Consider increasing blood pressure monitoring. Continue sorafenib dosing as scheduled.
Grade 2 asymptomatic and diastolic pressure 90-99 mm Hg	Begin anti-hypertensive therapy. Continue sorafenib dosing as scheduled.
Grade 2 (symptomatic/persistent) OR Grade 2 symptomatic increase by > 20 mm Hg (diastolic) or to > 140/90 mm Hg if previously within normal limits OR Grade 3	Sorafenib should be held ^a until symptoms resolve and diastolic blood pressure < 90 mm Hg; also treat subject with anti-hypertensives and when sorafenib is restarted, reduce by 1 dose level. ^b If diastolic blood pressure is not controlled (< 90 mm Hg) on anti-hypertensive therapy, reduce another dose level. ^b
Grade 4	Discontinue sorafenib

a: Subjects requiring a delay of > 30 days (modify according to study specific cycle length) should discontinue sorafenib unless, in the opinion of the treating physician, the subject may benefit from continued treatment.
 
b: Subjects requiring dose reductions beyond 400 mg once daily, every other day, should discontinue sorafenib.
	

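### The sorafenib dose-modification tables conflict or leave a gap in three places: febrile neutropenia (Table 2), raised systolic pressure (Table 6), and Grade 4 diarrhea or fatigue (Tables 3 and 4)

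*Combined protocol and SAP*

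**What the plan says.** **Table 2 (Section 6.2.1.2).** ANC below 0.5 is Grade 4: sorafenib is delayed until Grade 2 or less, then cut by two dose levels. ANC from 0.5 to below 1.0 is Grade 3: dosing stays on schedule with a cut of one level. Febrile neutropenia has its own row with no ANC limit: "Sorafenib held until toxicity has resolved to Grade 2 or less; when sorafenib is restarted, reduce by one dose level".

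**Table 6 (Section 6.2.1.5).** The text above the table treats as out of range "diastolic pressure > 90 mm Hg and/or systolic pressure > 140 mm Hg". One of the conditions leading to a hold is a rise "or to > 140/90 mm Hg if previously within normal limits". The hold ends when symptoms have gone and "diastolic blood pressure < 90 mm Hg; also treat subject with anti-hypertensives and when sorafenib is restarted, reduce by 1 dose level". The next step is "If diastolic blood pressure is not controlled (< 90 mm Hg) on anti-hypertensive therapy, reduce another dose level". The row that starts antihypertensive treatment without a hold is confined to asymptomatic Grade 2 with diastolic 90 to 99. Exclusion criterion 15 (Section 5.1.2) defines uncontrolled hypertension by systolic or diastolic pressure.

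**Tables 3 and 4 (Sections 6.2.1.3 to 6.2.1.4).** Table 3 takes Grade 4 non-hematologic toxicity off protocol therapy, but its title limits its scope: "excluding hypertension and hand foot skin reaction, diarrhea and fatigue". For diarrhea and fatigue, Section 6.2.1.3.1 says "The same dose-modification algorithm used for skin toxicities can be used to address these toxicities". The skin algorithm is Table 4, which has rows for Grades 1, 2 and 3 only.

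**The concern.** A dose-modification table should give each patient one action. Here identifiable patients get two actions, none, or a release that does not match the section's own description of abnormal pressure. Two clinicians following the text could then give similar patients different sorafenib exposure around and after the Y-90 procedure.

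Section 6.2.1.5 presents Table 6 as the schedule to follow and bars re-escalation after a reduction for hypertension, so the difference would last. Section 11.1 requires strict adherence to the protocol, which is hard to apply where the protocol gives two answers or none.

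**Working it through.** The plan states no figure on this point to reproduce. The check is to run example patients through the rows, then to size the groups from the protocol's own rates.

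**1. Table 2, febrile neutropenia**

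- ANC 0.3 with febrile neutropenia meets the Grade 4 row (delay, then two levels down) and the febrile row (hold, then one level down). By Table 1, from the starting dose of 400 mg twice daily, two levels down is 400 mg every other day (200 mg per day on average) and one level down is 400 mg once daily. The ratio is 400/200 = 2.
- ANC 0.7 with febrile neutropenia meets the Grade 3 row (no delay, one level down) and the febrile row (hold, then one level down). The reduction agrees, but one row continues dosing and the other interrupts it.
- The documents do not define febrile neutropenia by ANC and do not say which row governs.

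**2. Table 6, blood pressure.** Readings in a held patient on antihypertensives whose symptoms have resolved:

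| Reading (mm Hg) | Out of range by the section text | Meets release (diastolic < 90) | Triggers further reduction |
|---|---|---|---|
| 165/95 | yes, both | no | yes |
| 165/85 | yes, systolic | yes | no |
| 138/95 | yes, diastolic | no | yes |

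A patient who enters at 165/95 and whose diastolic alone falls to 85 moves from the first line to the second: still out of range, but released. The same holds for any reading with systolic above 140 and diastolic below 90. Such a reading also cannot use the antihypertensive-first row, which needs diastolic 90 to 99.

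**3. Grade 4 diarrhea and fatigue**

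- Table 3 has a Grade 4 row, but both events are outside its scope.
- Table 4 has no Grade 4 row, so neither table gives an action.
- Section 2.3 lists Grade 4 diarrhea with sorafenib at below 1%, so the case is foreseen. The documents give no Grade 4 rate for fatigue.

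**Size.** The maximum is 40 patients and 20 are already enrolled (Section 8.1), so new wording mainly reaches 40 - 20 = 20. Expected counts using the Section 2.3 rates:

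- Any hypertension, 9% to 17%: 0.09 × 20 = 1.8 to 0.17 × 20 = 3.4. This is a ceiling for the Table 6 problem, because the isolated-systolic share is not given.
- Grade 3/4 neutropenia, at most 5%: 0.05 × 20 = at most 1. The febrile share is not given.
- Grade 4 diarrhea, below 1%: 0.01 × 20 = fewer than 0.2. Taking 0.1% to 1% as an assumed range, the chance of at least one case in 20 is 1 - 0.999^20 = 2% to 1 - 0.99^20 = 18%.

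Section 1.1 reports no Grade 4 or 5 reactions in the first 20 patients and one Grade 3 hypertension, without saying whether that was systolic or diastolic.

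**The case against.** The best defense of Table 6 is that the section's range governs which readings are reported and criterion 15 governs entry. Neither is stated as a condition for ending a hold, and a diastolic-only release may be a deliberate clinical choice. The same cell also requires antihypertensive treatment and a one-level reduction at restart. That is fair, and a reader who infers that Table 6 is clinically wrong goes beyond the documents. What remains is a mismatch inside the table, between an entry condition that names systolic pressure and exit conditions that do not, with no reason given.

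For Table 2, one can say that the named febrile row governs over the general one. That is a possible reading, but it is not written down. It would also give a febrile patient a smaller reduction than an afebrile patient with the same ANC below 0.5, so a site could equally take the Grade 4 row as binding.

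For Grade 4 diarrhea, the tables are headed as recommended or suggested, the referral to the skin algorithm is permissive, Section 6.2.1.1 provides for delay or reduction for clinically significant related toxicity, and Section 5.2 allows withdrawal when continuing would be harmful. So it would be wrong to infer that the investigator cannot stop treatment. These provisions do not supply the missing row.

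A reader might also infer that the Section 8.1 toxicity monitoring is affected. The documents do not support that. The boundary counts patients with attributable non-hematological Grade 3 or higher events, so recurrence in a patient already counted adds nothing, and Table 2 places febrile neutropenia among the hematologic toxicities.

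Applying 9% to 17% to all 40 patients gives 3.6 to 6.8. That overstates the reach, because it counts every form of hypertension and includes patients already enrolled. Nor can a reading such as 175/80 be called Grade 3 from the documents, which do not reproduce the CTCAE blood-pressure cut-offs. The examples above do not need that grade.

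**Conclusion.** The point holds as a matter of internal consistency, with different strength in each part. Table 2 is a direct conflict: two dose levels, or two timings, for one patient. Table 6 is an unexplained mismatch between how raised pressure is recognized and how a hold is ended or a reduction extended. Tables 3 and 4 leave a gap at Grade 4 for diarrhea and fatigue.

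The reach is small: at most about 2 to 3 expected among the remaining 20 for Table 6, at most 1 for Table 2, and fewer than 0.2 for Grade 4 diarrhea. These counts assume that the sorafenib rates in Section 2.3 carry over to the combination. No sample size, stopping boundary or operating characteristic changes. The point still deserves correction, because the rules govern exposure to treatment and can be made consistent cheaply.

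**What to change.** - **Table 2:** reconcile the febrile neutropenia row with the Grade 3 and Grade 4 ANC rows, and state which governs when a patient meets two.
- **Table 6:** reconcile the entry, release and further-reduction conditions with each other, with the section's out-of-range text and with exclusion criterion 15, or state that leaving systolic pressure out is intended.
- **Tables 3 and 4 and Section 6.2.1.3.1:** reconcile them so that Grade 4 diarrhea and fatigue are covered by one named table.

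The content of each clinical rule is for the investigators to set. The cost is a wording amendment with the usual approvals. No new visits or data are needed, since Table 7 already schedules systolic and diastolic pressure, blood counts and adverse events.
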